## ETANT PREALABLEMENT EXPOSE QUE :

Le Docteur [name] développe une activité importante en chirurgie orthopédique, et que, dans ce domaine, il dispose de connaissances et d'un savoir-faire reconnus.

La Société DEDIENNE SANTE assure la fabrication et la distribution de prothèses et d'implants orthopédiques.

La Société DEDIENNE SANTE doit s'assurer de la qualité des résultats postopératoires obtenus avec les implants prothétiques qu'elle fabrique et distribue, notamment pour favoriser la valorisation technique et scientifique de ceux-ci, étant précisé que l'objet à court terme de cette convention est conforme à cet objectif.

Cette convention ne s'inscrit pas dans le cadre d'application de la loi HURIET, car il ne s'agit pas d'une expérimentation clinique prospective en vue de développer les connaissances biologiques et médicales mais de la validation d'un acte strictement thérapeutique. Elle répond aux critères d'une étude monocentrique puisqu'un seul centre a été chargé de suivre ce protocole.

## IL EST CONVENU ET ARRETE CE QUI SUIT :

### ARTICLE 1 : Mission

Le Docteur [name] accepte de réaliser, pour le compte de la Société DEDIENNE SANTE, l'activité de suivi post-marché décrite ci-après :

\* Produit(s) concerné(s) : SYMBOL CUP DMR HA et SYMBOL CUP DM CIMENTE

\* Nature des travaux. Recueil des informations objectives et quantifiées relatives à :

- la nature du diagnostic avant pose et l'indication retenue.
- le déroulement de l'intervention et le résultat opératoire obtenu.
- l'adéquation entre les tailles d'instruments et tailles d'implants
- l'évolution postopératoire à 1 an et 2 ans, notamment du positionnement et du comportement de ces implants.

Il est entendu que le Docteur [name] fera son possible pour assurer le suivi clinique de ses malades, afin que les résultats obtenus puissent être confirmés avec un plus grand recul clinique. Les informations seront consignées sur des cahiers d'observation spécifiques définis par la cellule d'évaluation clinique de la Société DEDIENNE SANTE, dont un exemplaire est joint à cette convention.

Cadre de l'étude :

Dans le cadre de la directive 93/42/CEE, il s'agit d'assurer le suivi clinique post-commercialisation d'un dispositif médical marqué CE, afin de vérifier la sécurité et les performances revendiquées pour les dispositifs médicaux. Cette étude va permettre de collecter des données cliniques nécessaires à toute évolution des produits fabriqués par la Société DEDIENNE SANTE.

Ce suivi porte sur 20 dossiers de patients ayant un recul minimum de 2 ans. Les résultats correspondants seront transmis à la Société DEDIENNE SANTE. Il s'agit d'une étude rétrospective observationnelle.

Il est expressément mentionné que l'accomplissement de cette mission ne limite en rien l'indépendance du praticien et n'est assortie d'aucune obligation d'utilisation ou de prescription des produits de la Société DEDIENNE SANTE.

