## 1. SUMMARY OF THE STUDY

TITLE	Retrospective Observational Cohort Study SYMBOL CUP 2
SHORT TITLE	SYMCOR-2
INVESTIGATOR	[name] [name]
SPONSOR	DEDIENNE SANTE S.A.S.
JUSTIFICATION / CONTEXT	Documentation of the clinical efficacy and safety of SYMBOL CUP DMR HA and SYMBOL CUP DM CEM dual mobility acetabular implants.
METHODOLOGY	Retrospective observational cohort study
MAIN OBJECTIVE	Estimate the safety of these implants under normal conditions of use
PRIMARY ENDPOINT	Implant survival rate at 2-year follow-up
SECONDARY OBJECTIVE	Estimate the efficacy of these implants under normal conditions of use
SECONDARY ENDPOINTS	
 
- Safety: Intra and extra-prosthetic dislocation rates
 
- Safety: Incidence of other adverse events
 
- Effectiveness: Harris Hip Score (HHS)
 
- Effectiveness: Devane classification
 
- Effectiveness: Charnley classification
 

INCLUSION CRITERIA	
 
- Any patient operated by [name] who has undergone hip replacement surgery with SYMBOL CUP DMR HA or SYMBOL CUP CEM acetabular implant.
 
- Patient having reach 2-year follow-up on March 01, 2018
 

NON-INCLUSION CRITERIA	
 
- Explicit refusal by the patient to allow data describing his pathology and treatment to be included in this study.
 
- Minor patients or patients under guardianship.
 

RESEARCH PROCESS	
Retrospective collection of clinical data:
 
 
- Recorded in the orthopedic surgery department's patient files, from the patient's pre-surgical assessment to the latest news at 2-year follow-up.
 
- Obtained by telephone interview for data up to 2-year follow-up, if the medical file does not provide all the source information. The telephone interview will be carried out by the investigator (or his secretariat) or by a clinical research associate delegated by the sponsor and approved by the investigator.
 

NUMBER OF SUBJECTS	Minimum total number of subjects: n=20
PLANNED NUMBER OF CENTERS	Single-center, single-investigator study

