### **4.1. DESCRIPTION OF MEASURES TAKEN TO REDUCE AND AVOID BIAS**

Consecutive recruitment with provision of sampling frame data.

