## **6. RÉALISATION PRATIQUE DU PROTOCOLE.**

### **6.1. DÉROULEMENT DES VISITES LIÉES A L'ÉTUDE**

The clinical research associate (CRA) delegated by the sponsor will make two or three visits to the investigational center:

- An inclusion visit to confirm the investigator's adherence to the protocol and to define the procedures for extracting and transferring anonymized data from the electronic patient record management system. As this is a single-center study, this visit will take place before the protocol is submitted to the CNIL.
- A visit to extract and transfer anonymized data from patient files, and to call patients to obtain their two-year follow-up data. On this occasion, patients will be informed that they may object to the inclusion of their information in this study. During this visit, the sponsor's clinical research associate will check that the data are consistent with the contents of the patient files. He/she will confirm the completeness of the cohort, with consecutive placement of dual-mobility acetabular implants. An anonymized list of all THA during the recruitment period will be obtained and checked to establish the sampling frame. This visit will take place at the start of the study.

- An additional visit by the CRA, to obtain missing data and resolve discrepancies, will take place if necessary.

In the event of death reported by the patient's entourage without a date, the surgeon will question the civil registry of the patient's commune of birth to obtain the date and cause of death.

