# **7. ELIGIBILITY CRITERIA**

## **7.1. INCLUSION CRITERIA**

Any patient operated by [name] who has undergone hip replacement surgery with SYMBOL CUP DMR HA or SYMBOL CUP CEM acetabular implant and having reach 2-year follow-up on March 01, 2018.

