## **10. STATISTICAL CONSIDERATIONS**

### **10.1. NUMBER OF SUBJECTS TO BE INCLUDED**

The size of the cohort considered to be the minimum in light of studies carried out by other manufacturers is at least 20 with a follow-up of 2 years.

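### The draft investigator contract scopes the follow-up at 20 files with no selection rule, while the protocol takes every consecutive eligible patient with 20 as a floor; the planned checks may miss a series cut short at either end

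*Combined protocol and SAP*

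**What the plan says.** **Contract.** Annex 5, Article 1: "Ce suivi porte sur 20 dossiers de patients ayant un recul minimum de 2 ans". In that sentence the word minimum attaches to the length of follow-up, not to the number of files. The annex is headed as a draft agreement.

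**Protocol, cohort size.** Section 1: "Minimum total number of subjects: n=20". Section 10.1 says the cohort "is at least 20 with a follow-up of 2 years".

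**Protocol, who is included.** Section 7.1 takes any patient of the named surgeon "who has undergone hip replacement surgery with SYMBOL CUP DMR HA or SYMBOL CUP CEM acetabular implant and having reach 2-year follow-up" by 1 March 2018. Section 4.1 gives the protection against bias as "Consecutive recruitment with provision of sampling frame data".

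**Protocol, checks.** Section 6.1 says of the sponsor's clinical research associate (CRA): "He/she will confirm the completeness of the cohort, with consecutive placement of dual-mobility acetabular implants". It adds: "An anonymized list of all THA during the recruitment period will be obtained and checked to establish the sampling frame". Section 10.5 runs the sampling frame from the first to the last inclusion date in the cohort. Annex 2 records, for each patient, the order number of the operation with that type of implant.

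**Not stated.** No section gives the number of eligible patients at the centre.

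**The concern.** The contract names a number and the protocol names a rule. They give the same cohort only if exactly 20 patients are eligible. Section 4 explains the single-surgeon design by the need for large consecutive series, so more than 20 is plausible, though not shown.

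The patients were treated before the protocol was written (section 7.3), so removals and dislocations are already known at the site when files are extracted. With a small cohort, one removal more or less visibly changes the primary result. Section 2.2 calls this the first clinical evaluation specific to these two cups and intends it for CE renewal and a reimbursement assessment. The report therefore has to show that the series is complete.

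**Working it through.** **1. The figure of 20.** Section 10.1 bases it on other manufacturers' studies. It gives no precision target, event rate or formula, and section 2.3 states no hypothesis. There is nothing to reproduce.

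**2. Can both documents be followed?** Let N be the number of eligible patients.
- N = 20: contract and protocol give the same cohort.
- N > 20: the protocol requires all N; the contract describes 20 and does not say which.

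Tables 3 and 4 give French sales for 2014 and 2015 of 15 + 194 + 19 + 172 = 400 units. That is a national total and does not give this surgeon's N.

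**3. What the planned checks would show.** Suppose, for illustration, that 30 patients are eligible and 20 files are extracted.

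| Files left out | Order number | Sampling frame (section 10.5) |
|---|---|---|
| Ten from inside the series | Gaps | Left-out operations fall inside the window and appear on the list |
| The last ten | No gap | Window closes at the last included patient; the ten fall outside |
| The first ten | Starts above 1 only if counted from the surgeon's first implant, which Annex 2 does not specify | Window opens at the first included patient; the ten fall outside |

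The list in section 6.1 covers the recruitment period, which that section does not define. If it is read as the section 10.5 window, it has the same blind spots.

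**4. Weight of one removal.** Ignoring censoring, one event moves crude survival by 1/n:
- n = 20: 1/20 = 5.0 points
- n = 30: 1/30 = 3.3 points
- n = 40: 1/40 = 2.5 points

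**5. Range of possible results.** N and the number of removals e are assumed. With all N patients, crude survival is 1 − e/N. When at least 20 patients have no removal, as in every row below, a set of 20 files can contain anywhere from 0 to e removals.

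| N | e | All eligible, 1 − e/N | Any 20 files |
|---|---|---|---|
| 25 | 2 | 92.0% | 90% to 100% |
| 30 | 2 | 93.3% | 90% to 100% |
| 40 | 2 | 95.0% | 90% to 100% |
| 60 | 3 | 95.0% | 85% to 100% |

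As a neutral benchmark, a random 20 would miss both of two removals with chance (N−20)(N−21)/[N(N−1)]:
- N = 25: 5×4/(25×24) = 3.3%
- N = 30: 10×9/(30×29) = 10.3%
- N = 40: 20×19/(40×39) = 24.4%

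The plan proposes no random draw; these figures only give scale.

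**6. Against sampling error.** With 0 removals in 20, the exact 95% upper limit for the revision risk is 1 − 0.025^(1/20) = 16.8%. The interval is wide, but it describes chance variation in a complete series and does not allow for files left out.

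**The case against.** A reader might infer that the contract caps the study at exactly 20 files and leaves the surgeon free to pick them knowing the outcomes. The documents do not support that.

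- The French wording describes scope. It contains no maximum and no instruction to stop, and the annex is a draft.
- The contract's preamble says that the single centre is charged with following this protocol, which points back to the consecutive rule.
- Article 2 provides no remuneration, so 20 is not a payment ceiling.
- Section 9 allows the CRA to copy the data on site, so extraction does not rest with the surgeon alone, although section 13.1 names only the investigator and team.
- The completeness check, the list of hip replacements and the order number, if applied, rule out free choice within the series.
- Eligibility closed on 1 March 2018, before protocol version 1.0 of 16 April 2018. Twenty may simply be the count the sponsor already expected.

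All of this stands, and it reduces the point to a mismatch with a conditional effect. It does not dispose of it. The checks are weak at the two ends of the series, and a CRA holding a contract for 20 files and a protocol for all eligible files has two standards of completeness, with no statement of which governs.

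**Conclusion.** The mismatch is real and should be resolved before extraction. If more than 20 patients are eligible, Annex 5, Article 1 and sections 4.1 and 7.1 cannot both be met, and a cohort cut off at either end could pass the planned checks.

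The size is conditional. If N is 20 there is no effect. Otherwise each removal included or omitted is worth 5 points at n = 20, 3.3 at n = 30 and 2.5 at n = 40; with two removals, a set of 20 files could report anything from 90% to 100%. These figures rest on assumed N and e and ignore censoring. Nothing in the documents shows that files were or will be selected by outcome.

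**What to change.** 1. Reword Annex 5, Article 1 so that the follow-up covers *all consecutive eligible files, at least 20*.
2. Define the cohort and the sampling-frame window in sections 7.1 and 10.5 by implantation date: either cup, this surgeon, from the first implantation to 1 March 2016 (two years before the cut-off of 1 March 2018). Section 7.1 does not state an implantation date, so the sponsor should confirm this reading.
3. Have the existing CRA check reconcile the extracted files to the surgeon's full list of these implants over that window.
4. Report the numbers eligible, included and excluded, with reasons.

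Section 10.1 needs no change, since it already states 20 as a minimum.

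Cost: one sentence in a draft contract, a date definition in two protocol sections, a sharper target for a visit already planned, and extraction of any eligible files beyond 20, which section 7.1 already requires.

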## ARTICLE 2 : Rémunération

Aucune rémunération au Docteur [name] n'est prévue pour cette évaluation.

## ARTICLE 3 : Organisation

Pour favoriser la réalisation de ce suivi, DEDIENNE SANTE mettra à la disposition du Docteur les moyens informatiques nécessaires :

- Cahiers d'observation, ou fichier numérique.
- L'organisation et les moyens statistiques de la Cellule d'Evaluation Clinique de DEDIENNE SANTE.

## ARTICLE 4 : COMMUNICATION

La présente Convention sera communiquée pour avis par DEDIENNE SANTE au Conseil Départemental de l'Ordre des Médecins. Selon la loi du 2002-2013 du 4 mars 2002 relative aux droits des malades et à la qualité du système de santé, l'avis du Conseil de l'Ordre sera considéré comme favorable si un avis défavorable n'est pas transmis à DEDIENNE SANTE.

DEDIENNE SANTE transmettra au Docteur [name] une copie de l'avis défavorable du Conseil de l'Ordre des Médecins, dans l'hypothèse de sa réception.

La présente Convention sera également portée, par le Docteur [name], à la connaissance du responsable de l'établissement dans les locaux duquel les travaux de suivi clinique seront opérés.

Les médecins hospitaliers ou hospitalo-universitaires, doivent en vertu du décret n° 2011-82 du 20 janvier 2011, obtenir l'autorisation du directeur de l'hôpital pour assurer une telle activité dite « accessoire ».

D'autre part, dans le souci de veiller au respect de la déontologie médicale les articles 4127-3 et 4127-5 du Code de la Santé Publique s'applique à cette Convention.

## ARTICLE 5 : Confidentialité

Suivant l'article R5121-13 modifié par le Décret n°2012-597 du 27 avril 2012, les investigateurs et les personnes appelées à collaborer aux essais, sont tenus au secret professionnel en ce qui concerne notamment la nature des produits étudiés, les essais, les personnes qui s'y prêtent et les résultats obtenus.

Ils ne peuvent, sans l'accord du promoteur, donner d'informations relatives aux essais qu'au ministre chargé de la santé, aux médecins inspecteurs de santé publique, aux pharmaciens inspecteurs de santé publique, au directeur général et aux inspecteurs de l'ANSM.

Les essais ne peuvent faire l'objet d'aucun commentaire écrit ou oral sans l'accord conjoint de l'expérimentateur ou de l'investigateur et du promoteur.

